**Table 4-6: Part 2: Single-Arm, Open-label Treatment Phase [Group B]**

Study Drug	Dosage Form	IP concentration	Dosing Frequency and Amount	Route of Administration
PRO 140 700mg	Parenteral solution	175 mg/mL	2 injections of PRO 140 (2 X 2 mL/inj.) up to Week 48	SC injection

Group A or Group B subjects that do not elect to participate in Part 2 of Treatment Phase and all Group C subjects who experience virologic failure (defined as two consecutive HIV-1 RNA levels of  $\geq 200$  copies/mL) at any time during the Treatment Phase will undergo the Virologic

Failure (VF) Visit assessments and then exit the Treatment Phase to enter the Follow-up Phase of the study.

Subjects who do not experience virologic failure will enter the Follow-up Phase of the study at the end of 48-week Treatment Phase.

All study subjects will re-initiate their previous antiretroviral regimen or an alternative regimen selected by their treating physician:

- One week prior to the end of 48-week Treatment Phase, or
- Anytime during the Treatment Phase, if virologic failure occurs or have met any other criteria for discontinuation of study treatment as specified in [Section 5.2.1](#) of the protocol. Subjects will be allowed to continue PRO 140 monotherapy while waiting for new ART regimen to be constructed by the Investigator.

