### 5.2 SUBJECT WITHDRAWAL

A subject who enters the Treatment Phase but does not complete the study, as defined in [Section 5.1](#), is considered to have prematurely withdrawn from the Study.

All subjects have the right to withdraw at any point during treatment without prejudice to future care. It will be documented whether or not each subject completed the clinical study. If for any subject, study treatment or observations were discontinued, the reason(s) will be recorded.

The Investigator can discontinue a subject at any time if it is considered medically necessary.

In addition, subjects WILL be withdrawn from the study, in consultation with the Medical Monitor and the Investigator, if any of the following are met:

- A subject is significantly non-compliant with the requirements of the protocol.
- The Investigator determines that it is in the best interest of the subject.
- Subject chooses to withdraw or is withdrawn due to an adverse event
- Recurring Grade 2 study drug injection related AE at two consecutive visits
- Occurrence of Grade 3 study drug injection related AE
- A subject becomes pregnant

**Note:** *The pregnancy will be followed to term for safety follow-up. Relevant safety information collected after the study has completed will be reported as supplemental information.*

- Discontinuation of study by Sponsor

Premature withdrawal from the study MAY occur if, in consultation with the Medical Monitor and the Investigator, any of the following are met:

- A subject is treated with a prohibited medication.

- Major protocol violation

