### 5.2.1 Discontinuation of Study Treatment

Discontinuation of study treatment (PRO 140) and resumption of previous or alternative antiretroviral regimen is recommended if:

- Subject experiences virologic failure (defined as two consecutive HIV-1 RNA levels of  $\geq 200$  copies/mL).

**Note:** *Subjects in Group A that experience virologic failure have option of re-initiating ART regimen or participating in Part 2 of Treatment Phase and receive higher dose of PRO 140 (525mg SC) weekly injection for remainder of 48-week Treatment Phase or until subsequent virologic failure event after viral re-suppression on higher dose.*

*Subjects in Group B that experience virologic failure have option of re-initiating ART regimen or participating in Part 2 of Treatment Phase and receive higher dose of PRO 140 (700mg SC) weekly injection for remainder of 48-week Treatment Phase or until subsequent virologic failure event after viral re-suppression on higher dose.*

- Develops AIDS-defining conditions as specified in Appendix I ([Section 17.1](#)) under which subject is unable to continue treatment with study drug (PRO 140), or subject require treatment with prohibited concomitant medications.
- Shows signs or symptoms of clinically significant immunosuppression
- Subject or the subject's clinician wishes to restart ART.
- Subject becomes pregnant.

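### Section 4.2 lets subjects stay on PRO 140 while new ART is arranged without excluding pregnancy, and the rules that stop injections at virologic failure do not mention this exception

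*Protocol*

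**What the plan says.** The permission stands in Protocol Section 4.2, below Table 4-6, in the list of occasions on which subjects return to ART. The second bullet applies at any time in the Treatment Phase "if virologic failure occurs or have met any other criteria for discontinuation of study treatment", with a pointer to Section 5.2.1. It then adds: "Subjects will be allowed to continue PRO 140 monotherapy while waiting for new ART regimen to be constructed by the Investigator". The bullet names no excluded criterion, no dose and no maximum interval.

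Section 5.2.1 says that stopping PRO 140 and "resumption of previous or alternative antiretroviral regimen is recommended if" one of five criteria is met: virologic failure, certain AIDS-defining conditions, clinically significant immunosuppression, a wish by the subject or clinician to restart ART, and pregnancy ("Subject becomes pregnant").

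Section 5.2 is stricter about the last of these: "subjects WILL be withdrawn from the study, in consultation with the Medical Monitor and the Investigator, if any of the following are met". Its list includes "A subject becomes pregnant". Section 1.6.1.4 adds that the risk to a fetus is not known and keeps pregnant women out of the study.

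Three other statements bear on the point. The note later in Section 4.2 sends subjects who meet a Section 5.2.1 criterion other than virologic failure to the T48 assessments and then to Follow-up. Section 4 stops weekly injections at virologic failure and names entry into Part 2 as the exception. The opening of Section 4.2 sets weekly dosing up to 48 injections, or until virologic failure if that comes sooner.

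**The concern.** Read literally, the bridging sentence reaches every subject who triggers its bullet, so it reaches a subject who becomes pregnant. A site that relied on the treatment section could give her further doses of an investigational antibody while a new regimen is put together, although the withdrawal section removes her from the study. What is at stake is avoidable fetal exposure to a product whose fetal risk the protocol describes as unknown.

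For virologic failure the stakes are lower. A short bridge may well be intended, to avoid a period with no antiretroviral at all. But a site reading Section 4, or the start of Section 4.2, would conclude that injections stop at failure unless the subject enters Part 2. A site reading further into Section 4.2 would conclude that they may go on. Sites could then treat the same situation differently, and the same dose could be recorded as a protocol deviation at one site and as permitted at another.

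**Working it through.** No figure in the plan bears on this point, so the check is a comparison of the text.

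1. **Who is covered by the permission?** The trigger is virologic failure or any other Section 5.2.1 criterion. The permission follows in the same bullet and speaks of subjects without qualification. The note later in the same section shows that the protocol can separate failure from non-failure cases when it wants to; the bullet does not.
2. **Is pregnancy among the criteria?** Yes. It is the last of the five in Section 5.2.1.
3. **What do the other sections require for the same event?**

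| Event | Bridging bullet, Section 4.2 | Other rules | Consistent? |
|---|---|---|---|
| Pregnancy | Further PRO 140 allowed while a new regimen is constructed | Section 5.2: withdrawal mandatory. Section 5.2.1: stopping recommended. Section 4.2 note: T48 assessments, then Follow-up | No |
| Virologic failure, not entering Part 2 | The same permission | Section 4: injections stop, Part 2 the only exception. Section 4.2 opening: dosing until failure. Section 5.2.1: stopping recommended | Not as worded; a cross-reference would reconcile them |

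4. **Does any rule switch the permission off for pregnancy?** Section 5.2 concerns withdrawal from the study and does not mention dosing. Withdrawal implies that study dosing ends, but the section does not refer to the bridging sentence. The Section 4.2 note gives an exit route and does not say that bridging is unavailable before or during it. No section is said to take precedence.
5. **Does any rule that stops dosing at virologic failure allow for bridging?** Section 4 names only Part 2. The opening of Section 4.2 names no exception; there the Part 2 route has to be taken from Section 4 or from the later note.

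The pregnancy conflict is the firmer of the two, because a permission meets a mandatory rule. The virologic-failure conflict is softer: Section 5.2.1 only recommends stopping, and waiting for a regimen ends of itself when the regimen starts.

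**The case against.** The strongest reply is that the permission is narrow and the specific rule should control. It applies only while a new regimen is being constructed. The same list distinguishes the previous regimen from an alternative one, so a pregnant subject who is still suppressed and can resume her previous drugs may have nothing to wait for. The note that follows sends her to the T48 assessments and Follow-up. Section 5.2 is mandatory and specific where the bridging sentence is general and permissive. Section 5.2.2 asks investigators to contact the medical monitor before stopping treatment, and Section 9.2 requires pregnancies to be reported to the sponsor. Most sites would probably stop.

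Much of this stands, and it lowers the likelihood of harm. It does not remove the contradiction: a pregnant subject who does need a new regimen falls within the permission as worded, and none of these provisions limits it.

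A reader might go further and infer three things that the documents do not support.

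- *That the permission is also wrong for AIDS-defining conditions and immunosuppression.* The AIDS-defining criterion already covers subjects who cannot continue PRO 140 or who need a prohibited medication, and a permission to continue does not oblige anyone to dose them. For immunosuppression, the alternative to a bridge may be a gap with no antiretroviral, since other ART is barred during monotherapy (Section 7.5.1). Bridging is a defensible clinical choice there.
- *That Sections 5.2 and 5.2.1 contradict each other on pregnancy.* One governs study withdrawal and the other treatment discontinuation. They point the same way and differ only in force.
- *That bridging after virologic failure is itself an error.* The fault is only that the rules ending injections do not mention it.

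**Conclusion.** The text is wrong as written on one narrow matter: Section 4.2 permits dosing in pregnancy that Section 5.2 rules out. A lesser inconsistency sits beside it, because the bridging exception is missing from the two statements that end injections at virologic failure.

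The problem should arise rarely. Pregnant women are excluded at entry, pregnancy tests at Screening and T1 must be negative, and two contraceptive methods are required of subjects of childbearing potential. The documents give no pregnancy rate and no expected wait for a new regimen. The sex ratios of earlier studies, or an assumed number of extra weekly doses, would therefore not measure how many subjects are affected, and no count is offered.

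The conclusion assumes that the bridging sentence is read as worded and that withdrawal under Section 5.2 means no further study drug. If the sponsor does intend bridging in pregnancy, the conflict remains and Section 5.2 is the place that would have to say so. No efficacy endpoint changes: virologic failure is settled by the two viral load results, before any bridging begins.

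**What to change.** - **Section 4.2, bridging bullet:** add that the permission does not apply to pregnancy, in which case PRO 140 stops and Section 5.2 governs.
- **Section 5.2.1:** make the pregnancy line mandatory rather than recommended, to match Section 5.2.
- **Section 4 and the opening of Section 4.2:** beside the rule that injections end at virologic failure, refer to the bridging exception. State that it is given at the subject's current dose and ends when ART starts.

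The cost is a few lines of protocol wording in Sections 4, 4.2 and 5.2.1. No visit, sample or SAP analysis is added.

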**Note:**

- Subjects may return to clinic for an additional blood draw in-between the clinic visits for plasma HIV-1 RNA levels, per the discretion of the Investigator.
- Virologic failure is defined as two consecutive levels of  $\geq 200$  copies/mL.
  - Subjects in Group A that experience virologic failure have option of re-initiating ART regimen or participating in Part 2 of Treatment Phase and receive higher dose of PRO 140 (525mg SC) weekly injection for remainder of 48-week Treatment Phase or until subsequent virologic failure event after viral re-suppression on higher dose.
  - Subjects in Group B that experience virologic failure have option of re-initiating ART regimen or participating in Part 2 of Treatment Phase and receive higher dose of PRO 140 (700mg SC) weekly injection for remainder of 48-week Treatment Phase or until subsequent virologic failure event after viral re-suppression on higher dose.
- Subjects who meet any criteria (other than virologic failure) for discontinuation of study treatment as specified in [Section 5.2.1](#) of the protocol, will undergo T48 Visit assessments and enter the Follow-up Phase of the study.
- Subjects who do not experience virologic failure will enter the Follow-up Phase of the study at the end of 48-week Treatment Phase.

Visits during the Treatment Phase will commence on T1, i.e. the date of first treatment, with weekly visits ( $\pm 3$  days) thereafter. The first Treatment Visit (T1) will take place as soon as HIV-

1 viral tropism, genotype and phenotype resistance results are available for review by Investigator, within 6 weeks of the Screening Visit.

#### 4.2.1 Treatment Phase: Treatment Visit-1 (T1)

The following assessments will be performed at T1 visit, unless otherwise specified:

##### Pre-Treatment

- Confirmation of eligibility criteria by reviewing test results and other criteria assessments performed at Screening Visit (see [Section 7.2](#) )
- Neurological Assessment (see [Section 7.8](#))
- Symptom-directed physical examination (see [Section 7.6](#))
- Change in concomitant medications (see [Section 7.5](#))
- Any changes in medical history since Screening Visit (see [Section 7.4](#))
- Vital Signs (see [Section 7.9](#))
  - **Note:** *Vitals will be taken twice: pre- and post-treatment. Post-Treatment Vital Signs will be assessed within 15 minutes following study treatment administration.*
- Collection of Blood Specimens (see [Section 7.10](#)) for
  - Plasma HIV-1 RNA level
  - TruCount T Assay
  - CCR5 Receptor Occupancy (IncellDx Lab)
  - HIV Drug Resistance Assay
  - PK sample for PRO 140
  - Anti-idiotypic antibodies to PRO 140
  - Blood sample for evaluation of potential biomarkers [*occurs at T1*]
    - gp120 genotypes
    - Plasma *HIV-1 RNA* Single Copy Assay
    - Immune Activation Markers
    - PhenoSense® Entry Assay [*performed at T1 using the blood sample collected for Tropism at Screening for subjects who are found eligible to be enrolled in the study*]
    - CCR5 expression levels

- Quest Diagnostics Proviral DNA® Tropism Assay [*if not performed at SV*]
- Cerebrospinal fluid (CSF) sample collection for Central Nervous System (CNS) sub-study (see [Section 7.10.16](#))
  - **Note:** CSF sample should be collected at T1 (prior to first dose of PRO 140), visit for subjects participating in CNS sub-study.
- Genital secretion sample collection for Genitourinary (GU) sub-study (see [Section 7.10.17](#))
  - **Note:** Genital secretion sample should be collected at T1 (prior to first dose of PRO 140) visit for subjects participating in GU sub-study.
- Urine Pregnancy Test (see [Section 7.10.8](#))

### **Administration of PRO 140**

PRO 140 is administered as subcutaneous injection in the abdomen weekly. A total of 350mg or 525 mg or 700mg (175 mg/mL) is delivered as two injections on opposite sides of the abdomen. The 350mg dose will be delivered as two injections of 1 mL each, 525mg dose will be delivered as two injections of 1.5 mL each or one injection of 3.0 mL, and 700mg dose will be delivered as two injections of 2 mL each.

**Note:** All treatment injections must be administered by a qualified medical professional (MD, DO, PA, LPN, LVN, NP, RN or CMA if permitted by state law) at clinic site or home visit or self-administered by subjects, for the duration of 48 weeks in the Treatment Phase.

### **Post-Treatment**

- Injection Site Reaction Assessment (see [Section 7.12](#))
  - **Note:** To assess injection site reactions, the Investigator will use the DAIDS AE grading table (refer to [Section 17.3](#)).
- Assessment of Adverse Events (AE) (see [Section 9](#))
- Vital Signs (see [Section 7.9](#)) will be assessed within 15 minutes of study treatment administration.

**Note:** Subjects will continue their existing antiretroviral regimen for one week after receiving initial dosing of PRO 140.

### **4.2.2 Treatment Phase: Treatment Visit-2 (T2) to Treatment Visit-16 (T16)**

The following assessments will be performed at each visit, unless otherwise specified:

- Assess for any Adverse Events and changes in Concomitant medications (see [Section 9](#) and [7.5](#)),
- Symptom-directed physical examination (see [Section 7.6](#)),
- Neurological Assessment (see [Section 7.8](#)) [*occurs at T16*]
- Vital Signs (see [Section 7.9](#))
  - **Note:** *Post-treatment vital signs will be assessed within 15 minutes following study treatment administration*
- Collection of Blood Specimens (see [Section 7.10](#)) for
  - Complete Blood Count at T12 visit
  - Biochemistry at T12 visit
  - Coagulation Indices [Prothrombin time (PT) and INR] at T12 visit
  - CCR5 Receptor Occupancy (IncellDx Lab)
  - Plasma HIV-1 RNA level
  - TruCount T Assay
    - **Note:** *Blood sample for plasma HIV-1 RNA level, TruCount T Assay, and CCR5 Receptor Occupancy should be collected at T2, T4, T6, T8, T10, T12, T14 and T16 visits when subject comes to clinic.*
  - Plasma HIV-1 RNA Single Copy Assay
    - **Note:** *Blood sample for plasma HIV-1 RNA Single Copy Assay should be collected at T8 and T12 visits when subject comes to clinic.*
  - Trofile DNA Assay and PhenoSense Entry Assay at T10 visit
  - PK sample for PRO 140
  - Anti-idiotypic antibodies to PRO 140
    - **Note:** *PK and ADA blood sample should be collected at T1 (prior to first dose), T4, T8, T12 and T16 visits.*
- Collection of Urine Specimen for Urinalysis (see [Section 7.10.15](#)) at T12 visit
- Measurement of treatment adherence (see [Section 7.14](#)) at T4, T8, T12 and T16 visits
- Study Treatment Administration (PRO 140)
  - Note:** All treatment injections must be administered by a qualified medical professional

(MD, DO, PA, LPN, LVN, NP, RN or CMA if permitted by state law) at clinic site or home visit or self-administered by subjects, for the duration of 48 weeks in the Treatment Phase.

- Injection Site Reaction Assessment (see [Section 7.12](#))
  - **Note:** *To assess injection site reactions, the Investigator will use the DAIDS AE grading table (refer to [Section 17.3](#)).*
- Subject-perceived Injection Site Pain Assessment (see [Section 7.13](#))
  - **Note:** *Subject-perceived injection site pain will be assessed using the Pain Visual Analog Scale (VAS) prior to study treatment administration assessing average pain at injection site since last treatment.*
- Cerebrospinal fluid (CSF) sample collection for Central Nervous System (CNS) sub-study (see [Section 7.10.16](#))
  - **Note:** *CSF sample should be collected at T4 visit for subjects participating in CNS sub-study.*
- Genital secretion sample collection for Genitourinary (GU) sub-study (see [Section 7.10.17](#))
  - **Note:** *Genital secretion sample should be collected at T4 and T16 visits for subjects participating in GU sub-study.*

#### 4.2.3 Treatment Phase: Treatment Visit-17 (T17) to Treatment Visit-48 (T48)

The following assessments will be performed at each visit during the remaining 32 weeks of the Treatment Phase, unless otherwise specified:

- Assess for any Adverse Events and changes in Concomitant medications (see [Section 9](#) and [7.5](#)),
- Symptom-directed physical examination (see [Section 7.6](#)),
  - **Note:** *Complete physical examination at T48*
- Neurological Assessment (see [Section 7.8](#)) [*occurs at T48*]
- Vital Signs (see [Section 7.9](#))
  - **Note:** *Post-treatment vital signs will be assessed within 15 minutes following study treatment administration*
- Electrocardiogram (ECG) (see [Section 7.7](#)) [*occurs at T48*]

- Collection of Blood Specimens (see [Section 7.10](#)) for
  - Complete Blood Count at least once every 12 weeks at T22-25, T34-37 and at T48 visits
  - Biochemistry at least once every 12 weeks at T22-25, T34-37 and at T48 visits  
Coagulation Indices [Prothrombin time (PT) and INR] at least once every 12 weeks at T22-25, T34-37 and at T48 visits
  - CCR5 Receptor Occupancy (IncellDx Lab)
  - Plasma HIV-1 RNA level
  - TruCount T Assay
    - **Note:** *Blood sample for plasma HIV-1 RNA level and TruCount T Assay should be collected at T17 and at least once every four weeks between T18-21, T22-25, T26-29, T30-33, T34-37, T38-41, T42-45 and T48 visits when subject comes to clinic.*
  - Trofile® DNA Assay [*occurs at T48*]
  - PK sample for PRO 140
  - Anti-idiotypic antibodies to PRO 140
    - **Note:** *PK and ADA blood sample should be collected at least once every four weeks between T18-21, T26-29, T34-37 and T42-45 visits, and at T48 visits.*
  - HIV-1 Drug Resistance Assay – GenoSure Archive [*occurs at T48*]
  - Blood sample for evaluation of potential biomarkers [*occurs at T48*]
    - Immune Activation Markers
    - PhenoSense® Entry Assay
- Collection of Urine Specimen for Urinalysis (see [Section 7.10.15](#)) at least once every 12 weeks at T22-25, T34-37 and at T48 visits.
- Measurement of treatment adherence (see [Section 7.14](#))
  - **Note:** *At least once every four weeks between T18-21, T22-25, T26-29, T30-33, T34-37, T38-41 and T42-45 visits followed by at T48 and VF visits when subject comes to clinic.*
- Study Treatment Administration (PRO 140)  
**Note:** All treatment injections must be administered by a qualified medical professional (MD, DO, PA, LPN, LVN, NP, RN or CMA if permitted by state law) at clinic site or

home visit or self-administered by subjects, for the duration of 48 weeks in the Treatment Phase.

- Injection Site Reaction Assessment (see [Section 7.12](#))
  - **Note:** *To assess injection site reactions, the Investigator will use the DAIDS AE grading table (refer to [Section 17.3](#)).*
- Subject-perceived Injection Site Pain Assessment (see [Section 7.13](#))
  - **Note:** *Subject-perceived injection site pain will be assessed using the Pain Visual Analog Scale (VAS) prior to study treatment administration assessing average pain at injection site since last treatment.*
- Re-initiate previous antiretroviral regimen or an alternative regimen selected by the treating physician at Week-47, if viral load remain suppressed.

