#### 4.3 VIROLOGIC FAILURE (VF) VISIT

Virologic failure is defined as two consecutive levels of  $\geq 200$  copies/mL.

Subjects in Group A or Group B that experience virologic failure have option of re-initiating ART regimen or participating in Part 2 of Treatment Phase and receive higher dose of PRO 140 weekly injection for remainder of 48-week Treatment Phase or until subsequent virologic failure event after viral re-suppression on higher dose.

The following assessments will be performed for all subjects who experience virologic failure during the Treatment Phase, prior to entering Follow-up Phase:

- Assess for any Adverse Events and changes in Concomitant medications (see [Section 9](#) and [7.5](#)),
- Complete Physical Examination (see [Section 7.6](#)),
- Vital Signs (see [Section 7.9](#)),
- Neurological Assessment (see [Section 7.8](#)),
- Electrocardiogram (ECG) (see [Section 7.7](#))
- Subject-perceived Injection Site Pain Assessment (see [Section 7.13](#)),
- Collection of Blood Specimens (see [Section 7.10](#)) for
  - Plasma HIV-1 RNA level
  - TruCount T Assay

- Complete Blood Count
- Biochemistry
- Coagulation Indices
- HIV Drug Resistance Assay (PhenoSense GT/Integrase)
- HIV Trofile® RNA Assay
- CCR5 Receptor Occupancy (IncellDx Lab)
- Anti-idiotypic antibodies to PRO 140
- PK sample for PRO 140
- Blood sample for evaluation of potential biomarkers [*occurs at T48*]
  - Immune Activation Markers
  - PhenoSense® Entry Assay
  - Quest Diagnostics HIV Co-receptor Tropism Assay
- CSF sample collection for CNS sub-study (see [Section 7.10.16](#))
  - **Note:** *CSF sample should be collected at VF visit for subjects participating in CNS sub-study.*
- Genital secretion sample collection for GU sub-study (see [Section 7.10.17](#))
  - **Note:** *Genital secretion sample should be collected at VF visit for subjects participating in GU sub-study.*
- Collection of Urine Specimen for Urinalysis (see [Section 7.10.15](#))
- Measurement of treatment adherence (see [Section 7.14](#))
- Re-initiate previous antiretroviral regimen or an alternative regimen selected by the treating physician

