## **7.6 PHYSICAL EXAMINATION**

The complete physical examination will include routine examinations for the following:

- General Appearance
- Head, Ears, Eyes, Nose, Throat (HEENT)
- Lymph Nodes
- Heart/Cardiovascular abnormalities
- Respiratory
- Abdomen
- Genitourinary
- Musculoskeletal and Extremities
- Neurologic abnormalities
- Dermatologic abnormalities
- Any other body system for which an abnormality is noted and which, in the opinion of the Investigator, is relevant to the safety of the subject or could impact safety or efficacy results for the subject; i.e., the abnormality is clinically significant (CS).

Each abnormality will be recorded and the Investigator will record an assessment of its clinical significance.

The complete physical examination will be conducted at the Screening Visit (SV), Treatment Visit 48 (T48), and at Virologic Failure (VF) Visit. Only symptom-directed physical examination will be performed at treatment and follow-up visits conducted within the clinic, and at unscheduled visits within the Treatment and Follow-up Phases.

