3.1.1 Safety Outcome Measures

The following metrics will be analyzed to assess the clinical safety of PRO 140 monotherapy regimen:

- Incidence of Treatment-Emergent Adverse Events (TEAE)
- Incidence of Treatment-Emergent Serious Adverse Events
- Incidence of Injection Site Reactions by Investigator evaluation
- Frequency of Grade 3 or 4 adverse events as defined by the DAIDS Adverse Event scale
- Tolerability of repeated subcutaneous administration of PRO 140 as assessed by study participants (using Visual Analogue Scale)
- Changes and shifts in laboratory measurements over time
- Changes in vital signs and weight over time
- Changes and shift in Electrocardiogram (ECG) parameters over time
- Incidence of Physical Examination abnormalities over time

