7. DATA CONVENTION AND RELATED DEFINITIONS

7.1 Baseline Definition

For all parameters, baseline will be defined as the last available value prior to initiation of the first dose of PRO140.

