8.2.1.4 Physical Examination

All physical examination findings will be listed and any abnormality will be summarized.

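### The physical-examination safety outcome counts any abnormality with no baseline comparison, so its rate can follow the type of examination rather than the subjects' condition

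*Protocol*

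**What the plan says.** SAP 3.1.1 includes "Incidence of Physical Examination abnormalities over time" among nine primary safety measures, and SAP 3.1 asks for each of them overall and within each dose group.

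Protocol 7.6 fixes the depth of examination: "The complete physical examination will be conducted at the Screening Visit (SV), Treatment Visit 48 (T48), and at Virologic Failure (VF) Visit". For the rest, "Only symptom-directed physical examination will be performed at treatment and follow-up visits conducted within the clinic". The visit sections agree. T1, before the first dose, has a "Symptom-directed physical examination" (Protocol 4.2.1); the last treatment visit has "Complete physical examination at T48" (4.2.3); the VF Visit has "Complete Physical Examination" (4.3).

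The SAP's whole method is one sentence: "All physical examination findings will be listed and any abnormality will be summarized" (SAP section headed Physical Examination, numbered 8.2.1.4, a number also used for Clinical Laboratory Evaluations). Protocol 8.7.5.4 says the same. By contrast, the SAP gives laboratory values change from baseline and shift tables, vital signs change from baseline by visit, and ECG both change from baseline and shift tables.

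SAP 7.1 defines baseline for every parameter: "baseline will be defined as the last available value prior to initiation of the first dose of PRO140".

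**The concern.** An incidence over time needs either comparable ascertainment at each time or a rule for what counts as new. The plan gives neither for physical examination. A long-standing finding seen at the complete screening examination may go unrecorded at symptom-directed visits and then be recorded again at T48 or VF. Under the SAP sentence it counts there as an abnormality like any other.

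No untreated arm could expose this. Every subject receives PRO 140, and the first ~150 were enrolled in a single arm. The subject's own screening examination is the only reference for what was present beforehand, and the SAP does not call for it. A reader of the table could take a late rise for an effect of prolonged treatment or of virologic failure.

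**Working it through.** The documents give no figure to reproduce, so the check is of logic, with an illustration on assumed values.

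**Inputs from the documents.** Complete examination at screening, T48 and VF; symptom-directed at T1 and at later clinic treatment visits before T48; any abnormality counted.

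**Assumed inputs.** A constant proportion p of subjects has a pre-existing abnormality. A complete examination detects all of them and a symptom-directed examination detects a fraction s. There is no drug effect and no true change. The documents give neither p nor s, so a range is shown.

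**Formulas.**
- Reported rate at screening, T48 and VF: p
- Reported rate at symptom-directed visits: p × s
- Spurious rise from symptom-directed visits to T48 or VF: p − p × s = p × (1 − s)
- Change from screening to T48 or VF: p − p = 0

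| p | s | Symptom-directed visits (p × s) | T48 or VF (p) | Spurious rise p × (1 − s) |
|---|---|---|---|---|
| 10% | 10% | 1% | 10% | 9 points |
| 10% | 30% | 3% | 10% | 7 points |
| 10% | 50% | 5% | 10% | 5 points |
| 20% | 10% | 2% | 20% | 18 points |
| 20% | 30% | 6% | 20% | 14 points |
| 20% | 50% | 10% | 20% | 10 points |
| 30% | 10% | 3% | 30% | 27 points |
| 30% | 30% | 9% | 30% | 21 points |
| 30% | 50% | 15% | 30% | 15 points |

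The range is 5 to 27 points. In every row the change from the screening examination is 0.

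**Which baseline.** The last examination before dosing is the symptom-directed one at T1. If SAP 7.1 is read that way, change from baseline at T48 or VF is again p × (1 − s), the full 5 to 27 points. If it is read by body system, a system not examined at T1 has no T1 value, the last available value is from screening, and the spurious change is 0. The SAP does not say which reading applies.

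**Dose groups.** Completers are examined completely at T48 and subjects who leave treatment for virologic failure at VF. Under Protocol 4.2, those who stop for other listed reasons undergo the T48 assessments. Each should therefore have one complete examination after dosing starts, at a time that depends on failure. Rescued Group A or B subjects may have a second one (VF, then T48 or another VF Visit); Group C has no rescue option. With failure proportion v and rescue uptake r, Groups A and B average 1 + v × r such examinations against 1 in Group C. At assumed v = 30% and r = 50% that is 1 + 0.30 × 0.50 = 1.15.

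**The case against.** The strongest reply is that the safety consequence is largely handled elsewhere. Under Protocol 9.1, examination findings that the investigator considers clinically significant and that occur after first treatment are reported as adverse events, and worsening of an existing condition also qualifies. Under Protocol 7.4, earlier events go to medical history. The treatment-emergent tables thus already separate new from old for findings that matter most. This stands and limits the point. It does not repair the outcome itself, because findings judged not clinically significant are kept out of adverse events, while the examination summary takes in everything.

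A second reply is that the SAP labels nothing as new, and that a table showing the same rate at screening and at T48 would look unchanged. That is fair if a screening row is shown. But equal totals do not show that the same subjects are abnormal: findings that resolved and findings that arose can cancel. The SAP sentence also does not specify a by-visit layout; that is inferred from the outcome's own wording. A pooled summary would remove the late step but still count pre-existing findings.

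Third, all analyses are descriptive and no decision rule rests on this outcome. That is correct; no error rate or power figure is affected.

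A reader might infer more than the documents support:
- **Every abnormality at T48 or VF is false incidence.** Even with no true change, the excess over symptom-directed visits is p × (1 − s), not p, and it is 0 against screening.
- **SAP 7.1 definitely makes T1 the baseline.** It is one reading of an ambiguous rule.
- **Dose comparisons are seriously biased.** Most subjects have one later complete examination whatever their course, so the groups differ mainly in its timing.
- **Every visit outside screening, T48 and VF has a symptom-directed examination.** Protocol 7.6 ties that examination to clinic and unscheduled visits. Dosing may be at home, and the 6- and 12-month follow-up visits list no examination.

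**Conclusion.** The concern holds for the summary as the SAP words it. Pre-existing findings are counted, and the reported rate can rise at T48 or VF solely because a complete examination replaces a symptom-directed one. The size is unknown from the documents. It is 5 to 27 points if p is 10–30% and s is 10–50%, assuming constant prevalence and full detection at a complete examination. Adding a change-from-baseline line alone may not cure it, because SAP 7.1 leaves open whether T1 or screening is the baseline. The damage is mainly to one descriptive primary safety outcome. The documents do not support a claim that clinically significant new findings would be lost or that the dose comparison is invalid.

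**What to change.** In the SAP section headed Physical Examination:

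1. Name the complete screening examination as the baseline for this outcome, as an explicit exception to SAP 7.1.
2. Tabulate, by dose group and body system, the shift from screening to the complete examination at T48 or VF, in three categories: normal, abnormal but not clinically significant, and clinically significant.
3. Where a rescued Group A or B subject has more than one later complete examination, use the first (VF at the assigned dose) for the assigned-dose table and show the later one separately. The protocol is not explicit that subjects moving to rescue have a VF Visit at the first failure. The SAP should report how many lack that examination and keep a complete examination made on the rescue dose out of the assigned-dose table.
4. List symptom-directed findings separately and keep them out of the same incidence.
5. State the timing of the complete examination alongside the table, since the shift table keeps the difference in timing between subjects with and without failure.

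The cost is SAP wording and one shift table. Protocol 7.6 already has each abnormality and its clinical significance recorded, so no extra examinations are needed.
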